	
 • All patients will have arterial mapping to provide the surgeons with a surgical plan based on the preoperative mpMRI. • Video-recorded BL NVB sparing RARP performed by [name], [name], [name] or [name]. • All patients will receive the same penile rehabilitation plan that is the standard of care at UCLH. • Patients with an APA identified will be offered a postoperative MRI angiogram to assess patency of APA. • As an optional part to the study, patients will be offered a penile doppler before and/or after their surgery to assess erectile haemodynamics. • The feasibility study will be able to inform the barriers for recruitment in a future appropriately powered study.
STUDY TIMELINES	
Study Duration/length	2 years
Expected Start Date	December 2025
End of Study definition and anticipated date	December 2027 The end of the study is defined as the date of the final 12-month follow-up visit for the last recruited participant. Recruitment will stop once between 20 and 40 patients have been enrolled, and all participants will be followed for 12 months after surgery.
Key Study milestones	
Submission for REC and HRA approval
 
Acquire REC and HRA approval
 
Start recruiting patients
 
Complete full 40 patient data with follow-up up to 1 year.

FUNDING & OTHER	
Funding	Non-acquired.
Other support	Clinical research fellow- [name]
STORAGE of SAMPLES / DATA (if applicable)	
Human tissue samples	Non-applicable
Data collected / Storage	UCLH/ UCL one drive secure storage data storage
KEY STUDY CONTACTS	
Chief Investigator	[name] , Honorary Associate Professor [contact] [name]
Study Coordinator	
Sponsor	University College London
Funder(s)	Non
Committees	
Sub-contractors	Non-applicable
Other relevant study personnel	N/A

KEY ROLES AND RESPONSIBILITIES

SPONSOR: The sponsor is responsible for ensuring before a study begins that arrangements are in place for the research team to access resources and support to deliver the research as proposed and allocate responsibilities for the management, monitoring and reporting of the research. The Sponsor also must be satisfied there is agreement on appropriate arrangements to record, report and review significant developments as the research proceeds, and approve any modifications to the design.

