1.2.4 Preoperative mpMRI, mapping of pelvic vasculature and postoperative MRI

mpMRI is accepted as the gold standard for preoperative local staging of PCa. In addition to diagnosis and staging, mpMRI helps guide surgery and the degree of NVB sparing without impacting margin status (34).

Prior research in this area has focused on utilising the pre-surgical mpMRI information to predict the recovery of continence(35). For example, membranous-urethral length (MUL), measured using the preoperative mpMRI, is an established independent predictor for postoperative recovery of urinary continence (36,37). This information informs preoperative patient counselling and treatment decision-making. However, the literature on imaging markers to predict and mitigate the risk of ED in patients with PCa undergoing minimally invasive radical prostatectomy has not been summarised before.

We carried out a systematic review (PROSPERO; Registrations ID CRD 42022359557) to evaluate the possible application of imaging parameters to predict EF after RARP. Nevertheless, the variability of results, significant risk of bias, and inadequate study design in the available literature render the therapeutic use of the reported parameters of low utility. Good-quality, prospective research is needed to further evaluate a variety of imaging parameters as predictors of postoperative EF to ensure results are reproducible. There has been no assessment of accessory pudendal artery identification through imaging preoperatively and correlation of this to EF outcomes after surgery. The prevalence of accessory pudendal artery is 38.2% (8). In our studies at UCLH we were able to map the accessory pudendal arteries of men using prostate mpMRI (unpublished material). We are currently looking at identifying the accuracy of the mpMRI in identifying the APA (unpublished material).

Several studies have shown that vasculature of the pelvis can be mapped. Selective pudendal angiography can be used to demonstrate the presence of accessory pudendal arteries; however, this is an invasive procedure (38). Moreover, contrast enhanced MR angiography can be used to identify accessory pudendal arteries(39).

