Primary end-points	
 1. Recruitment and Retention Rates 
 a) Percentage of patients who satisfy the eligibility criteria amongst patients who opted for RARP b) Percentage of patients consenting to participate (denominator= number of eligible patients approached) c) Percentage of participants completing the study (denominator=number of patients consenting for the study) 2. MRI Assessment Feasibility 
 -Time required for APA mapping on mpMRI 3. Intraoperative Video Analysis

	
 -Percentage of RARP procedures with complete, analysable video recordings (denominator= number of patients consenting for the study) -Time required for video analysis of APA preservation 4. Erectile Function Questionnaire Completion 
 -Completion rates of validated EF questionnaires such as the International Index of Erectile Function (IIEF) questionnaire & EPIC -26 sexual domain within patients consenting to join the study. -Time taken to complete the questionnaires 5. Post-operative MRI assessment feasibility 
 -Proportion of patients who accepted to have a 3-month follow-up MRI angiogram within patients consenting to join the study -Proportion of patients who have a patent APA 6. Baseline Penile Doppler US (PDUS) assessment feasibility 
 -Proportion of patients accepting to have a preoperative PDUS. -Proportion of patients who received a baseline Doppler scan. 7. Postoperative PDUS assessment feasibility 
 -Proportion of patients who accepted to have a postoperative PDUS -Proportion of patients who received a postoperative PDUS

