3.7 Assessment of the pelvic vasculature with a postoperative an MR angiogram

By obtaining an MR angiogram with an arterial phase after the surgery, we will be able to confirm whether there is blood flow in the accessory pudendal arteries after surgery. This additional MRI at least 3 months after surgery will be only offered to patients who have an accessory pudendal artery on their preoperative mpMRI. This will be useful to assess whether the APA patency after surgery has an effect on EF outcomes. If there is an incidental finding on this MRI relating recurrence, then the parent team and the CI will be notified promptly. This will lead to further appropriate action.

We will follow an established and validated protocol for MRI angiography on month 3 (described in Appendix)

3.8 Penile doppler US (optional): Objective assessment of EF using erectile haemodynamics.

Penile Doppler ultrasound (PDUS) is a well-established diagnostic tool for ED in specialist clinical practice. As an optional part to the study, we will offer patients an opportunity to assess their erectile haemodynamics prior to surgery through a PDUS. The APA presence, features or absence will be known through review of their preoperative mpMRI. With that knowledge, the optional PDUS before surgery will outline the effect of APA on the haemodynamics in healthy men with prostate cancer.

Patients who will not respond to PDE5i after surgery will be offered with a PDUS to evaluate the flow of penile arterial blood and to provide objective evidence that the underlying cause of ED is arterial.

This will be an optional part to the study and will be offered at 6 months or earlier if patients wish to have ICI to treat their ED. This is the accepted standard of care for the evaluation of post-RARP ED that is not responding to medical treatment.

The standard penile doppler US protocol will be followed for patients who opt for this assessment. Details of the protocol are provided in appendix.

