Patients who have an APA identified on their preoperative mpMRI that are undergoing a bilateral NVB sparing RARP will be offered an additional MRI angiogram at 3 months to assess the patency of the accessory artery. All other aspects of their care will be the same including the preoperative andrology consultation, recording of their intracorporeal surgery as well as post operative care.

End of study

The end of the study is defined as the date of the final 12-month follow-up visit for the last recruited participant. Recruitment will stop once between 20 and 40 patients have been enrolled, and all participants will be followed for 12 months after surgery.

Table 1: showing Study specific schedule as well as standard clinic schedule

	Study specific schedules	Standard clinical schedule	Study specific assessments	Routine clinical assessments
Preoperative mpMRI prostate		X		
Prostate Biopsy		X		
Multidisciplinary meeting		X		
Clinic appointment to discuss treatment options		X		

Clinic appointment for patient decision: for surgery		X		
Radiology preoperative MRI meeting: for NVB surgery, identify APA	X (identify APA~)	X		
Eligibility assessment by study team	X~			
Preoperative andrology telephone clinic		X	IIEF-EFD, EPIC-26	IIEF-EFD, EPIC-26
Consent for research	X			
Pre-assessment for surgery		X		Routine bloods and assessments.
Optional: Penile doppler before)			X	
Surgery: RARP		X	Consent for research	
First surgical follow up appointment 6 weeks		X		
Andrology appointment at 6 weeks, 6, 12 and 24 months.		X	IIEF-EFD, EPIC-26	
Routine cancer and surgical follow up at 3 months		X		All patients: PSA, Patients with ED: Testosterone, HbA1c, lipid profile

~ This is done by the study team and does not constitute an additional visit by the patients.

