11 ASSESSMENT AND MANAGEMENT OF RISK

-Data management risks are discussed in section 10.

-Video recordings: This will be done through the standard operating stack and require no additional steps to changes to standard care. Currently, the procedures are routinely recorded in the operating room for training purposes and to evaluate where improvements could be made. The management of the video data file is discussed in section 10.

-Hospital visits: for participating patients, an additional MR angiogram will be obtained postoperatively for study participants which will require an additional visit to the hospital. The remaining appointments will align with the standard andrology follow-up after radical prostatectomy.

-Penile dopplers (OPTIONAL) A penile doppler US will be offered to patients before and after surgery to assess the erectile machinery for study participants. This will be particularly useful for patients that fail to achieve satisfactory erections with medical treatment after surgery. A large proportion of patients that fail medical treatment and wish to escalate their erectogenic treatment will require injection treatment to the side of the penis. During the tutorial for this therapy, we will carry out a penile doppler ultrasound to assess their EF objectively and assess the blood flow to the penis.

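### Primary end-point 5 counts men who are never offered the postoperative MR angiogram as not accepting it, so its acceptance figure is capped at the APA prevalence in the sample

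*Protocol*

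**What the plan says.** The Protocol defines the first part of primary end-point 5, in the Study Summary and again in Section 2, as the "Proportion of patients who accepted to have a 3-month follow-up MRI angiogram within patients consenting to join the study". The denominator is therefore stated, in the same words in both places.

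The offer of the scan is narrower:

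- Section 3.7: the additional MRI "will be only offered to patients who have an accessory pudendal artery on their preoperative mpMRI".
- Study Summary, methodology key points: "Patients with an APA identified will be offered a postoperative MRI angiogram to assess patency of APA".
- Section 4, Additional visits: men with an APA on the preoperative mpMRI who are having bilateral NVB sparing surgery "will be offered an additional MRI angiogram at 3 months to assess the patency of the accessory artery". The Postoperative MRI paragraph of the same section carries the same restriction.

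The eligibility criteria in Section 5 do not require an APA, and the study title covers men with and without one. On frequency, Section 1.2.4 states: "The prevalence of accessory pudendal artery is 38.2" (per cent). The lay summary in Section 1.1 says up to a third. The target is 20 to 40 men.

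The second part of end-point 5 is the "Proportion of patients who have a patent APA", with no denominator given. One sentence in Section 11 reads more broadly than the rest: "an additional MR angiogram will be obtained postoperatively for study participants which will require an additional visit to the hospital".

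**The concern.** An acceptance rate should be the share who say yes among those who were asked. Here most of the denominator is expected never to be asked, and each of those men enters the calculation exactly as a refusal would.

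Section 1.2.7 (Feasibility assessment) makes the practicality of the postoperative MR angiogram one of the things this study must establish for a later powered study. A reader who takes end-point 5 at face value would conclude that men are reluctant to have the scan when they may all have agreed. Two feasibility cohorts with identical willingness would also report different figures merely because they contained different numbers of men with an APA.

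The Protocol uses a base that fits the question elsewhere: the consent rate in end-point 1b is divided by eligible men approached, not by all men listed for surgery. End-point 5 does not follow that logic.

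**Working it through.** The Protocol gives no expected acceptance figure, so there is nothing of its own to reproduce. The check is an identity followed by binomial arithmetic.

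**Inputs.** N = 20 or 40 consenting men (Section 3). APA prevalence p = 0.382 (Section 1.2.4), with 1/3 as the alternative (Section 1.1). Acceptance among men offered is assumed at 100%, 80%, 60% and 50%.

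**Identity.** Let m be the consenting men with an APA, all of them offered the scan, and a the number who accept.

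End-point as written = a/N = (m/N) × (a/m) = observed prevalence × acceptance.

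Since a cannot exceed m, the end-point cannot exceed m/N. If only some of the m men are offered the scan, the cap is lower still.

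**Expected value of the end-point as written.**

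| Acceptance among men offered (assumed) | p = 0.382 | p = 1/3 |
|---|---|---|
| 100% | 38.2% | 33.3% |
| 80% | 0.382 × 0.8 = 30.6% | 26.7% |
| 60% | 0.382 × 0.6 = 22.9% | 20.0% |
| 50% | 0.382 × 0.5 = 19.1% | 16.7% |

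**Chance variation of the ceiling.** This is the central 95% range of m from Binomial(N, p).

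| N | p | Expected m | 95% range of m | Ceiling m/N |
|---|---|---|---|---|
| 20 | 0.382 | 7.6 | 4 to 12 | 20% to 60% |
| 40 | 0.382 | 15.3 | 9 to 21 | 22.5% to 52.5% |
| 20 | 1/3 | 6.7 | 3 to 11 | 15% to 55% |
| 40 | 1/3 | 13.3 | 8 to 19 | 20% to 47.5% |

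**One value, several explanations.** A reported 19.1% fits 50% acceptance at 38.2% prevalence, 76.4% at 25%, or 100% at 19.1%. The end-point alone cannot separate them.

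**Worked examples (Clopper-Pearson 95% intervals).**

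| Sample | Divided by all consenting men | Divided by men with an APA who were offered |
|---|---|---|
| 40 men, 15 with an APA, 12 accept | 12/40 = 30% (17% to 47%) | 12/15 = 80% (52% to 96%) |
| 40 men, 15 with an APA, 15 accept | 15/40 = 37.5% (23% to 54%) | 15/15 = 100% (78% to 100%) |
| 20 men, 8 with an APA, 6 accept | 6/20 = 30% (12% to 54%) | 6/8 = 75% (35% to 97%) |

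In the first example the two intervals do not overlap.

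**The case against.** The strongest defence is that the all-consenting base is a legitimate quantity. Scans accepted per man enrolled, multiplied by planned enrolment, gives the scans, visits and cost that the full study must provide for. The same base is used in end-points 1c, 3 and 4, so it may be a deliberate common denominator. This stands as far as it goes: the figure is useful as a yield. It is not acceptance, which is what the end-point names. It would therefore be wrong to infer that the end-point tells the full study nothing.

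Nor is the information lost. APA prevalence is a separate secondary end-point, and the log in Section 3.1 counts men who consent to and undertake the angiogram. Dividing one proportion by the other returns acceptance, provided every man with an APA was offered the scan. That proviso matters. Section 4 ties the offer to men having bilateral sparing surgery, and neither the Section 3.1 log nor the Section 4 recruitment logbook lists how many were offered the scan. The recovery is therefore approximate.

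Other stronger readings are tempting and are not supported:

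- *The study would report failure on this end-point.* The Protocol attaches no success threshold or progression criterion to it, so a low figure triggers nothing.
- *The end-point measures prevalence instead of acceptability.* It is the product of the two and moves with both.
- *The ceiling is 38%.* That is only its expected value; the actual ceiling is whatever prevalence the sample shows.
- *The patency line is also wrong.* It has no stated base, and a missing analysis denominator may be left to an analysis plan. Patency can in any case be seen only in scanned men with an APA.
- *Section 11 shows that everyone is scanned.* It is one loosely worded sentence about extra visits, set against consistent restrictions in the Study Summary and Sections 3.7 and 4.

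**Conclusion.** The point holds as a mismatch between a stated denominator and a stated restriction on the offer. Primary end-point 5, followed literally, gives a misleadingly low acceptability figure: about 38%, 31% or 23% when true acceptance is 100%, 80% or 60%, with a ceiling that chance alone could place between 20% and 60% (20 men) or 23% and 53% (40 men).

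These sizes rest on the Protocol's 38.2% prevalence, on assumed acceptance rates, and on every man with an APA being offered the scan. At a prevalence of one third the reported figures fall to about 33%, 27% and 20%. The structural point, that the end-point cannot exceed the observed prevalence, needs none of these assumptions beyond the restricted offer itself.

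It should be corrected because it is a primary end-point whose written definition does not deliver what it names. The consequence is misreading rather than a wrong decision: no decision rule depends on it, and the underlying quantity is approximately recoverable.

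**What to change.** 1. In primary end-point 5 (Study Summary and Section 2), set the acceptance denominator to consenting men with an APA on the preoperative mpMRI who were offered the MR angiogram.
2. In the Section 3.1 log, add the number of men offered the scan. This is the one new item to record.
3. Keep scans accepted per consenting man as a separate yield count, labelled as such.
4. As tidying only: reconcile the Section 11 sentence with the Study Summary and Sections 3.7 and 4, and state that patency is reported among men with an APA who were scanned.

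The cost is a wording change and one extra log field, with no added visits or procedures. The statistical price is precision: the base falls from 20 to 40 men to about 8 to 15 expected (4 to 21 across the two 95% ranges at 38.2% prevalence). In the 40-man example, the interval widens from 17% to 47% (30 percentage points) to 52% to 96% (44 points). The wider interval is centred on the right quantity.

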3 STUDY DESIGN & METHODS OF DATA COLLECTION

This is a prospective single centre non-interventional feasibility study. This research will recruit from patients with localized PCa waiting for RARP at University College London Hospitals.

In this prospective feasibility study, we will obtain patient demographic/ medical history and outline imaging parameters from the preoperative mpMRI. Functional outcomes will be measured using validated PROMs and an optional penile doppler for patients who prefer to have intracavernosal injections to treat their erections.

We aim to approximately recruit 20-40 patients into our research study. The study will include individuals in their 18 or older. We will recruit patients who have good EF based (IIEF-EFD ≥ 24 , PDE5i naive) prior to the procedure. Patients undergoing bilateral NVB spare RARP will have the opportunity to participate in this research if they wish. The eligibility criteria are discussed in detail in section 6. All patients will have IIEF-EFD and EPIC -26 completed prior to surgery and 6 weeks, 6 and 12 months.

FIGURE 2 shows the the recruitment process as well as the timeline of this prospective non-interventional study

Participants will join the study with at least 24 hours to review the information sheet and provide consent to be part of the research project.

Sampling strategy:

Our study will employ a consecutive sampling approach over a 12-month period. All consecutive patients in that timeframe who are eligible to participate in the study will be offered to join the study.

Study duration: Recruitment will be for 12 months and at duration will be least 12 months for the primary outcome with a secondary outcome at 24 months follow-up.

3.1 Data collection:

We will collect the following data and keep a log about the number of patients:

1. eligible for the study
2. consenting to be enrolled in the study
3. completing all baseline questionnaires, questionnaires at the set time points.
4. consent and undertake a PDUS at baseline
5. with successful intracorporal video retrieval during RARP
6. consent and undertake a PDUS postoperatively
7. consent and undertake an MRI angiogram postoperatively

Data will be collected through:

1. Review of patient medical and operative hospital records: Standardized data collection forms: will be used to record observations and extract data from medical records.
2. Direct patient observation: Patients will be followed for at least 12 months
3. pre-surgical prostate mpMRI
4. surgical video recordings
5. Functional outcomes including EF and continence using validated tools at baseline and 6 weeks, 6, 12 and 24 months.
6. Postoperative MRI for patients with an APA identified.
7. Optional: pre and postoperative penile doppler US

3.2 Data variables:

List the variables to be collected:

- A. Ethnicity, occupation, age.
- B. Past medical and surgical history (hypertension, diabetes, high cholesterol, obstructive sleep apnea, previous prostate benign surgery, smoking history and pack years, medications exclusions: IHD, CVA, PVD)
- C. body mass index
- D. blood tests to diagnose any metabolic cause for ED
 - a. lipid profile
 - b. testosterone
 - c. HbA1c
- E. Assessment of preoperative mpMRI (see section 3.3)
- F. Operative documentation:
 - a. Time in minutes, blood loss

- b. Nerve spare grade
 - i. Laterality
 - ii. Interfascial vs intrafascial
 - iii. High or low release
- c. Different surgical approaches (yes or no) Anterior fascial spare, bladder neck spare, complete urethral preservation, intraprostatic urethral preservation, Mansouri approach.
- G. Assessment of intracorporal video recordings (see section 3.4)
- H. Functional outcomes using validated tools (see section 3.5)
- I. Oncological outcomes i.e. final histology, post-operative PSA and salvage treatment if any.
- J. Postoperative MRI angiogram for patients with APA (see section 3.7)
 - a. Vasculature assessment postoperatively
- K. Optional: assessment of erectile haemodynamics (see section 3.8)
 - a. Peak systolic velocity and end diastolic velocity
 - b. Before and after RARP

3.3 Assessment of preoperative mpMRI:

The pelvic vascular anatomy exhibits significant variations among individuals, which will be mapped out during this study using the diagnostic preoperative mpMRI. Existing classification systems will be used to categorize the origin, trajectory, dimensions, and branching patterns of the prostate arteries, pudendal arteries, and other accessory arteries supplying the penis (18,45).

This will be carried out by at least 2 blinded dedicated uro-radiologists with expertise in interventional vascular radiology and PCa. The assessors will be blinded to the patient, operative details, surgeon and functional outcomes of the surgery.

The MRI quality will be outlined mainly through assessment of the dynamic contrast enhancement sequence. Poor quality MRI will be excluded from the study based on enhancement phase field of view and ability to visualize contrast up to the cavernosal arteries.

List of variables collected through pre-operative MRI review and surgical planning parameters by two expert uro-radiologists:

- a. Prostate volume
- b. Prostate morphology (median lobe)
- c. findings related to difficult dissection i.e. pelvic lipomatosis, fistulas, pelvic fractures
- d. Pudendal artery presence and diameter
- e. Prostate artery presence and classification
- f. Accessory pudendal artery presence and origin
- g. Cavernosal arteries

The resulting classification will be displayed in a tabular format, facilitating visualization and comparison of the variations noted among different subjects. These categories will be used to examine their association with EF recovery and treatment response at 6 weeks, 6 months and 12 months.

3.4 Assessment of intracorporal video recordings:

The outcomes of EF recovery are influenced by the quality of NVB sparing surgery. This has the potential to confound our study results. Consequently, we will objectively evaluate the efficacy of NVB sparing surgery by employing the validated PACE questionnaire (33).

Assessment of NVB sparing through recorded videos:

Robotic surgery provides video documentation of the entire procedure only of the abdominal/pelvic parts of the patients. There will be no recording of any of the exterior body part of the patients with identifiable features. These recordings will be used to evaluate and analyze the specific techniques employed in NVB-sparing RARP. The videos will be obtained from the laparoscopic stack in the operating theatres (SDC3 by Stryker) already in place at UCLH theatres. Data security handling is outlined in Section 11.

The assessment will be carried out by at least two independent high-volume radical prostatectomy surgeons, for each annotated video to evaluate interobserver variability. The external assessors will be blinded to the patient, operating surgeon and the patient outcomes.

For the assessment, the surgeons will use a standardized framework to annotate the videos, employing key performance indicators aligned with the domains of the PACE tool, which will be modified to suit NVB assessment. Each NVB (e.g., two assessments for patients undergoing bilateral NVB sparing) will be evaluated using a Likert scale for each domain.

Relevant data points, such as the time taken for specific tasks, error rates, and adherence to the surgical protocol, will be manually extracted from the annotated videos.

3.5 Assessment of functional outcomes:

Patient reported outcomes of EF and urinary continence:

Evaluation of outcomes will be carried out using validated questionnaires. EF will be assessed using an ED screening tool, IIEF-EFD and EPIC-26. Urinary continence will be assessed using the EPIC-26 continence domain.

Participants will receive the questionnaires prior to surgery (baseline), week 6, month 6, 12 and 24. These time points correspond to the normal appointment schedules provided to patients under the post-RARP penile rehabilitation.

Participants will fill in the form on paper or electronically and this will be transferred to the database by the research clinical fellow. Data protection measures are outlined in section 11.

We will use RedCap platform to offer patients a chance to complete the questionnaires through an electronic platform either via email or smartphone.

3.6 Controlling surgical confounders:

3.6.1 Sources of confounders:

The confounders of EF recovery are categorized into three categories: pre-surgical, surgical, and post-surgical. Comorbidities and baseline erectile functions are pre-surgical confounders. The quality of bilateral NVB sparing and intraoperative surgical complications are surgical confounders. The patient's overall well-being, post-surgical complications, and penile rehabilitation are all post-surgical concerns. Further to these patients can develop metabolic conditions (during their follow-up) contributing or exacerbating their ED.

3.6.2 Management of confounders:

To control the pre-surgical confounders the study is focusing on men with no pre-existing ED and no established vascular disease that increase the likelihood of ED (IHD, PVD, CVD)

The surgical confounders will be adjusted for by limiting the surgeons in the study and measuring the quality of the NVB sparing and intraoperative complications.

The post-surgical confounders will be balanced by administering a standardized, proven post-surgical penile rehabilitation protocol that is used by UCLH Urology. The protocol is provided is described in 1.2.5.

The post-surgical complications will be captured during follow-ups and the overall well-being will be captured through the validated tools administered. Appropriate statistical tests will be applied to adjust for these confounders. Patients who have ED will be investigated with routine blood tests to screen for metabolic causes of ED and will be accounted for in ad-hoc data analysis.

Further details of statistical analysis and methods employed to adjust for confounders are provided in the data analysis section.

